Peer counselling is being introduced worldwide in supporting mothers' needs for successful maintenance of breastfeeding. Findings from a Cochrane review suggest that postnatal care at home may reduce infant health service utilization in the weeks following the birth, and that more home visits may encourage more women to exclusively breastfeed [7]. In high resource settings healthy women and babies are frequently discharged from hospital within one or two days of birth, potentially home visits in the first few days of the birth by healthcare professions or trained support workers offer opportunities for assessment of the mother and new born, health education, infant feeding support, emotional and practical support.[8-11] By having existing trained peer counsellors (PC) by La Leche League (HK) from our previous project, we propose to conduct a (web-based) home-based peer support programme for mothers who intend to breastfeed but have a low self-efficacy in breastfeeding. We understand mothers are often housebound and find it difficult to attend group support or seek help during the first month postpartum which is the critical period in sustaining exclusive breastfeeding and are at high risk in developing postpartum depression. Peer supporters help women overcome their breastfeeding problems, and women report improved mental health through increased self-esteem, confidence and well-being [12].

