As intervention involves peer support (face-to-face) and no invasive procedures will be involved, risks to women and their infants are likely to be minimal. In terms of confidentiality and anonymity, analysis will take place on anonymous data. Personal identifiable data will be held separately from the anonymous data used for analysis.

Benefits include women gaining in awareness of the value of breastfeeding for their own and for their infant's health, and feeling supported in this aspect of caring for their infants.

1 Objectives and Purpose

The aim of the proposed study is to evaluate the effectiveness of a (web-based) home-based breastfeeding peer support program in improving breastfeeding practices among women with low breastfeeding self-efficacy.

2 Design

This is a two armed blinded randomized controlled trial. 442 women will be recruited from four hospitals. Trained peer counsellors will provide home based (web based due to 5th Covid wave) one-to-one breastfeeding intervention sessions to the participants.

Study Procedure

1. Recruitment:

Mother-infant pairs will be recruited from a hospital that has an average of 300+ deliveries per month. Eligible participants will be approached and invited to join the study in antenatal clinics. Women who agree to participate and sign the consent form will be invited to complete the following forms available both in Chinese or English version:

- a. Demographic Data Collection Form
- b. Breastfeeding Self-efficacy and Attitude Data Collection Form

Research assistant will complete the following form from participants' medical records:

- a. Maternal and Birth Data Collection Form

This study includes two study arms:

- a. Home-based peer support programme (web-based) and standard usual care
- b. Control group will be standard usual care

Participants will be randomized following completion of the baseline data. Block randomization procedures with random block sizes of 2, 4 or 6 will be used. An independent research assistant who will not participate in participant recruitment, data collection and analysis will generate the allocation sequence using the statistical software Stata 14. Allocation sequences will be kept in sequential numbered, opaque, sealed envelopes. Outcome assessors will be blinded to the treatment allocation. The research assistant will draw the first sealed envelope from the box and participants will be allocated to that intervention group.

2. Telephone follow-up call:

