The team members have successfully trained 60 PCs from our previous project. The training programme comprised of 20 hours of classroom teaching and practical sessions at Queen Elizabeth Hospital and the Maternal Child Health Centres (MCHCs). The training programme was conducted by UNICEF and La Leche League covering topics such as (1) why breastfeeding is important, (2) how to assure good start of breastfeeding, (3) how to help mother breastfeeding (4) communication skills, (5) common breastfeeding problems, (6) diet and hygiene, (7) maternal illness and needs, (8) local support and role of peer counsellors. The peer counsellors were assessed by their trainers after completing the training programme. Those who pass the assessment can then carry out volunteer work using the train the trainer approach with supervision from La Leche League in MCHCs. Additional training workshop will be arranged for the PCs on solving problems of exclusive breastfeeding and correct breastfeeding technique by team leaders.

The intervention will be based on the PC programme previously conducted in our project except it will be home based (web based) peer support programme by trained PCs. In order to ensure the quality and consistency of intervention, additional training tailored to issues that may encounter in (web-based) home-based contacts will be provided to peer counsellors before the study.

The (web-based) home-based PC programme comprises of two schedules of two contacts during first month postpartum, one contact during 2 months postpartum, one contact during 4 months and one contact during 6 months postpartum, when mothers are most likely to experience difficulties with breastfeeding, and thereafter as needed. Both control and intervention groups will receive the same standard antenatal and postpartum care and a breastfeeding information leaflet. The control group will not receive home based PC programme but a breastfeeding information leaflet so the subjects will be blinded to the nature of the interventions.

5 Assessment of Efficacy

This study aims to assess effectiveness of the peer support intervention. The assessment of efficacy of the intervention will be undertaken at 1 month, 2 months, 4 months and 6 months postpartum using the criteria specified in the study outcomes.

6 Assessment of Safety

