This research involves a patient support intervention and we do not anticipate any patient safety issues. The person(s) carrying out the intervention will be trained and with experience in supporting breastfeeding women. However, as a precaution, both the delivery of the intervention and participant outcomes will be closely monitored by the PI and the study investigators

7 Statistic

Data Analysis

To compare the baseline characteristics between the two study groups, t-tests will be used for continuous variables and chi square test for categorical variables. Intention to treat analysis will be conducted. The primary outcome analyses will compare the proportions of participants in the two study groups exclusively breastfeeding at 1, 2, 4 and 6 months postpartum using chi square tests. To control for confounding factors, multiple logistic regression models will be used if required to compare breastfeeding rates between groups at the study follow up points. The secondary outcome analyses will use an independent 2-sample t tests to examine the breastfeeding self-efficacy scores and EPDS scores between the two study groups at baseline and at 1 and 3 months postpartum. To control for confounding factors, multiple linear regression models will be used to compare the scores between the groups at 3 months.

Where appropriate, each estimate will be accompanied by a 95% confidence interval and a 5% level of significance will be used in all statistical tests except where specified. The analysis will be performed using the Stata version 14.0 statistical software.

8 Direct Access to Source Data/Documents

Once data are collected, only the PI will have access to named data which will be kept locked in the PIs office in the School of Nursing. Access to the study data will be available for study related monitoring, audit and regulatory inspection by appropriate bodies. It will also be available for IRB review as appropriate.

9 Quality Control and Quality Assurance

As part of the usual review process in the department, data analysis will be reviewed by the study team to ensure it is appropriate, accurate and correctly interpreted.

10 Ethics

The main ethical considerations for this study are to ensure confidentiality to the participants and to ensure that the participants feel free to either participate in the study or to not participate in the study. The following measures will be taken to address these concerns:

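### The planned tests and regressions ignore peer-counsellor clustering in the intervention arm; if counsellors differ in effectiveness, confidence intervals are too narrow and type I error can exceed 5%

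*Combined protocol and SAP*

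**What the plan says.** All references are to the combined protocol and SAP.

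- **Size and allocation.** Section 2 (Design) states that "442 women will be recruited from four hospitals". Under Study Procedure, "Block randomization procedures with random block sizes of 2, 4 or 6 will be used". The allocation ratio is not given. Two arms and even block sizes imply 1:1, so about 221 women per arm.
- **Who delivers the intervention.** Background Information bases the programme on an existing resource: "By having existing trained peer counsellors (PC) by La Leche League (HK) from our previous project". Section 4 (Treatment of Subjects) gives the size of that pool: "The team members have successfully trained 60 PCs from our previous project". It adds that "Those who pass the assessment can then carry out volunteer work". The number of counsellors active in this trial, the rule for assigning women to them, and whether a woman keeps the same counsellor are not stated.
- **How it is delivered.** Section 2 describes "one-to-one breastfeeding intervention sessions to the participants". Section 4 schedules repeated contacts from the first month to six months postpartum. The control arm gets usual care and a leaflet, with no counsellor.
- **How it is analysed.** Section 7 (Statistic) compares the proportions "exclusively breastfeeding at 1, 2, 4 and 6 months postpartum using chi square tests". Self-efficacy and depression scores are compared by independent two-sample t-tests. Logistic and linear regressions are planned only to adjust for confounders. There is no counsellor term, random effect, robust standard error or ICC.
- **What is recorded.** None of the data collection forms named under Study Procedure is described as capturing the counsellor's identity.

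**The concern.** Women supported by the same counsellor share her skill, availability and persistence. If counsellors differ in these respects, outcomes within a counsellor's caseload are correlated, and the intervention arm carries less information than 221 independent women would. The control arm has no such structure, so the trial is partially nested: clustered in one arm and not in the other.

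The usual standard error for the difference omits the between-counsellor component. It is then too small, and intervals for the breastfeeding, self-efficacy and depression outcomes after randomisation are too narrow. The counsellor is the main ingredient of the intervention, so variation between counsellors bears directly on how far the result would carry over to others delivering the same programme. If counsellor identity is not captured during the trial, the question may not be answerable afterwards.

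**Working it through.** **The plan's own figures.** The relevant ones are 442 women and a 5% significance level. The 442 cannot be reproduced, because no power, target difference or dropout is stated. The 5% is reproduced when there is no clustering: the formula below gives 5.0% at ICC = 0, and simulation gave 5.0% to 5.1%.

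**Is sharing unavoidable?** With 1:1 allocation, 442/2 = 221 intervention women. If only the pool of 60 is used, 221/60 = 3.7 women per counsellor on average. Sharing then follows from the documents' own numbers.

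**Formulas.** For k counsellors with equal caseloads m = 221/k, one counsellor per woman, equal outcome variance in the arms, and counsellors regarded as a sample of those who might deliver the programme:

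- Design effect in the intervention arm: DE = 1 + (m − 1) × ICC
- True over naive standard error of the difference: r = √((1 + DE)/2), because only one arm is inflated
- Actual two-sided type I error at nominal 5%: 2 × (1 − Φ(1.96/r))

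**Worked example, ICC 0.05.**

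- 60 counsellors: DE = 1 + 2.683 × 0.05 = 1.134; r = √(2.134/2) = 1.033; 1.96/1.033 = 1.897; type I error 5.8%.
- 20 counsellors: m = 11.05; DE = 1 + 10.05 × 0.05 = 1.5025; r = √(2.5025/2) = 1.119; 1.96/1.119 = 1.752; type I error 8.0%.

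**Range of type I error.** The ICC and k are assumed; neither is in the documents.

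| Counsellors | Women each | ICC 0.02 | ICC 0.05 | ICC 0.10 |
|---|---|---|---|---|
| 60 | 3.7 | 5.3% | 5.8% | 6.6% |
| 40 | 5.5 | 5.5% | 6.3% | 7.7% |
| 20 | 11.05 | 6.2% | 8.0% | 11.0% |
| 10 | 22.1 | 7.5% | 11.3% | 17.2% |

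**Check by simulation.** There were 200,000 trials per setting, with a mean rate of 33% in both arms, beta-binomial counsellor effects in the intervention arm only, and an uncorrected chi-square test. For ICC 0.02, 0.05 and 0.10 this gave 5.3%, 5.8% and 6.6% with 60 counsellors, and 6.2%, 8.1% and 10.9% with 20. Both agree with the formula.

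**Interval width.** At ICC 0.05 the correct interval is 3% wider than the naive one with 60 counsellors and 12% wider with 20. The total needed to match the precision of 442 independent women is 442 × 1.067 ≈ 472 with 60 counsellors and 442 × 1.251 ≈ 554 with 20.

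**Unequal caseloads.** These raise the figures. With an assumed coefficient of variation of 0.7, 20 counsellors and ICC 0.05: DE = 1 + (1.49 × 11.05 − 1) × 0.05 = 1.773; r = 1.178; type I error 9.6%.

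**Does the remedy work?** With cluster-robust standard errors, 60 counsellors at ICC 0.05 gave 4.9%. For 20 counsellors at ICC 0.05, two sets of simulations gave 5.3% (4,000 trials) and 5.9% (20,000 trials). The error was 6.2% for 20 counsellors at ICC 0.10 and 7.3% for 10 at ICC 0.05. Robust errors alone therefore remain somewhat too small when counsellors are few.

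**The case against.** A reader might infer that every comparison in this trial has intervals that are too narrow and a type I error above 5%. The documents do not support that, for these reasons.

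- **The consequence is conditional.** It requires counsellors to differ, and no ICC is given. If counselling affects no woman at all, the test keeps its 5%, because women are individually randomised and the counsellor adds nothing to their outcomes. The excess arises when the average effect is zero but some counsellors do better than others. The interval-width point does not depend on the null: it also holds when there is a true effect that varies by counsellor.
- **It is small at the only documented number.** With 60 counsellors and ICC up to 0.05, type I error is at most 5.8%. The larger figures need fewer active counsellors, a higher ICC, or both. Section 4 lets only those who passed assessment go on, but gives no pass rate and no number active here.
- **Sixty is not a stated ceiling.** The text does not rule out counsellors from outside that pool.
- **One counsellor per woman is an assumption.** If contacts rotate between counsellors, the clustering changes form and may weaken.
- **Variation may be limited.** Section 4 plans extra training for consistency, and Section 6 plans close monitoring of delivery. Both favour the lower end of the ICC range.
- **Baseline comparisons are unaffected.** Baseline scores are collected before randomisation and before any counsellor contact.

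All of these stand as limits on the size and certainty of the problem. None shows that the ICC is zero, and none puts the counsellor into the analysis.

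**Conclusion.** The point holds in conditional form and is minor to moderate in size. The trial is partially nested by design, and the analysis in Section 7 ignores this. If counsellors differ in effectiveness, intervals for the post-randomisation comparisons are too narrow. When the average effect is zero but counsellors vary, type I error over ICC 0.02 to 0.10 is 5.3% to 6.6% with 60 counsellors and 6.2% to 11.0% with 20.

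This rests on 1:1 allocation, a two-sided test, equal caseloads, one main counsellor per woman and no dropout. The ICC and the number of active counsellors are assumed throughout. The documents do not establish that the error rate will in fact exceed 5%. The case for changing the plan is that the remedy is cheap and, without counsellor identity on record, the matter could not be checked later.

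**What to change.** 1. State how many counsellors will deliver the programme, how women are assigned to them, and whether a woman normally keeps the same one.
2. Record the ID of the first-allocated counsellor for each intervention woman. Defining clusters by first allocation keeps the analysis by intention to treat, even if counsellors change later.
3. In Section 7, analyse the post-randomisation outcomes with logistic models (feeding status) and linear models (scores) that allow for counsellor clustering in the intervention arm only. Use either cluster-robust standard errors with each control woman as her own cluster, or a partially nested mixed model. Prespecify a small-sample correction if about 20 or fewer counsellors deliver the programme.
4. Report the simple chi-square and t-tests alongside, and leave the baseline comparisons as they are.

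The cost is one data field and one option in the Stata models that the plan already foresees. The interval will be about 3% to 12% wider at ICC 0.05 (60 to 20 counsellors), and wider still if the ICC is higher or fewer counsellors are active. If counsellors often rotate, first allocation describes the clustering only approximately, and the report should say so.

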The participants will receive follow-up telephone calls at one, two, four and 6 months postpartum. Each follow-up call will take approximately 15 minutes.

The following forms will be completed by a research assistant in the telephone follow-ups:

One month follow-up:

- a. One-Month Follow-up Data Collection Form

Two months follow-up:

- a. Two-Month Follow-up Telephone Data Collection Form
- b. Breastfeeding Self-efficacy and Attitude Data Collection Form

Four months follow-up:

- a. Four-Month Follow-up Telephone Data Collection Form
- b. Breastfeeding Self-efficacy and Attitude Data Collection Form

Six month follow-up:

- a. Six-Month Follow-up Telephone Data Collection Form

These data collection forms will be completed if needed:

- b. Weaning Data Collection Form (if participants' babies have been weaned)
- c. Return to Work Data Collection Form (if participants have return to work)

Data Sources

Data collection will consist of: (1) baseline demographic data will include data such as education, income, employment, family composition, antenatal education, (2) maternal and infant data which will include data on the mother's previous obstetrical history, delivery data and basic infant health data.

Study Outcome

Primary outcome: Infant feeding status.

Key Measures

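### The protocol says a leaflet blinds the mothers, but both arms receive it and only one arm gets peer contacts, so intervention mothers are not blinded

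*Combined protocol and SAP*

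**What the plan says.** Three statements bear on blinding.

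- Section 2 (Design) opens with an unqualified label: "This is a two armed blinded randomized controlled trial".
- The recruitment procedure in the same section names one blinded group: "Outcome assessors will be blinded to the treatment allocation".
- Section 4 (Treatment of Subjects) adds a second group. Controls do not get the peer programme but are given "a breastfeeding information leaflet so the subjects will be blinded to the nature of the interventions".

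The sentence just before that last one reads "Both control and intervention groups will receive the same standard antenatal and postpartum care and a breastfeeding information leaflet". The intervention arm also has peer counsellor contacts in the first month, then "one contact during 2 months postpartum, one contact during 4 months and one contact during 6 months postpartum", and more as needed.

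On measurement, the section on telephone follow-up says "The participants will receive follow-up telephone calls at one, two, four and 6 months postpartum" and "The following forms will be completed by a research assistant in the telephone follow-ups". The primary outcome is infant feeding status. Section 7 (Statistic) will "compare the proportions of participants in the two study groups exclusively breastfeeding at 1, 2, 4 and 6 months postpartum using chi square tests".

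**The concern.** A leaflet given to everyone cannot conceal the one component that differs between the arms. A mother who has scheduled conversations with a peer counsellor knows that she is getting peer support, yet section 4 refers to the subjects without limiting the word to controls, and section 2 labels the whole trial blinded.

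This matters because the outcomes come from the mother. Whether an infant has had any water, formula or solids is known to the caller only through what she says; no objective check is described. The self-efficacy scale (BSES-SF) and the depression scale (EPDS) are likewise her own answers. A mother who knows that she has been supported to breastfeed may describe her feeding differently from one who has not. Blinding the caller protects how the answer is recorded, not how it is given. A report that repeated the protocol's wording would tell readers that the primary comparison is better protected than it is.

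**Working it through.** No figure in the plan needs reproducing here. The check sets what each arm receives beside what is said about blinding.

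**Step 1: what differs between the arms.**

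| Component | Intervention | Control | Source |
|---|---|---|---|
| Standard care | yes | yes | Section 4 |
| Leaflet | yes | yes | Section 4 |
| Scheduled peer contacts | at least 5 | 0 | Section 4 |
| Sham or attention contact | not applicable | none described | Section 4 |
| Outcome telephone calls | 4 | 4 | Telephone follow-up call |

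The contact count is 2 + 1 + 1 + 1 = 5, for month 1 and then 2, 4 and 6 months. The month-1 wording could also mean two sets of two contacts, giving 4 + 1 + 1 + 1 = 7. On either count the control figure is 0, and the peer contacts are the only scheduled difference.

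**Step 2: what each blinding statement can cover.**

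- *Outcome assessors.* Stated as blinded to allocation. Nothing in the documents contradicts this as a plan.
- *Intervention mothers.* The leaflet is common to both arms, so it carries no information that could mask the contacts. These mothers cannot be unaware of the support that they receive.
- *Peer counsellors.* They deliver the programme, so they are not blinded to it.
- *Control mothers.* They may or may not know what the other arm receives. Section 10 (Ethics) requires written consent from all participants, but the text supplied does not show what they are told about the two arms.

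**Step 3: whether assessor blinding closes the gap.** The chain for the primary outcome is mother's knowledge, mother's answer, caller's record. Assessor blinding acts on the last link only. Outcome calls fall at 1, 2, 4 and 6 months. Peer contacts are scheduled in month 1 and at 2, 4 and 6 months. A call may therefore come close to a contact, and a mother may mention it. The forms listed in the protocol include no stated item for recording that.

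**Step 4: size.** The documents give no rate of over-reporting for either arm and no validation of maternal report. Any figure for the resulting bias would rest on assumed reporting rates and on base rates from a feasibility study that randomised 20 women. The conclusion uses no such figure.

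**The case against.** The best defence is that the clause has been read too broadly. Its sentence is about the control group, and it speaks of the nature of the interventions, whereas the statement on assessors speaks of allocation. It may mean only that control mothers are not told what is being contrasted. That is plausible and cannot be excluded, because the consent material is not in the text supplied. It could save the clause for control mothers. It does not save the unrestricted reference to the subjects or the unqualified label in section 2, since intervention mothers still know what they receive.

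A second defence is that mothers cannot be masked to peer support in a trial of this kind, and that the workable protection, assessor blinding, is already planned. This also stands: the design is not at fault for being open to the mother. The fault is in saying otherwise.

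A reader might go further and infer any of the following, none of which the documents support.

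- *That control mothers are unblinded too.* The text does not say what they know.
- *That the primary result will be biased towards the intervention.* No evidence of differential reporting is given. Over-reporting by controls would work against the intervention, so the direction is open.
- *That assessor blinding is broken because a research assistant both draws the envelopes and completes the follow-up forms.* The documents do not say that this is one person, and the assessor-blinding statement implies that it is not.

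**Conclusion.** The point holds for intervention mothers and peer counsellors: the protocol claims a blinding that its own description of the arms rules out. It remains open for control mothers. The conclusion rests only on the description of the arms and on the outcomes being the mother's own report; it needs no assumption about reporting rates.

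The consequence is an overstated protection of the primary comparison, together with the two self-reported scales. Its numerical size is unknown and its direction is not determined. It does not invalidate the trial or call for a different design. It should be corrected because the statement is wrong as written, concerns a self-reported primary outcome, and costs very little to put right.

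**What to change.** 1. In section 2, replace the bare label with a description such as: randomised, outcome-assessor blinded; intervention mothers and peer counsellors not blinded.
2. In section 4, replace the leaflet clause with a statement limited to control mothers that says what they are told about the other arm. Deleting the clause outright could discard a masking of controls that may be real.
3. Add one item to the follow-up forms on which the caller records any unblinding during the call.
4. When interpreting the primary result, acknowledge that reporting bias is possible and could run in either direction.

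A sensitivity analysis for reporting bias is optional. If one is done, it should allow over-reporting in either arm, not only among intervention mothers.

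The cost is wording in two sections, one form item and a sentence of interpretation. The planned 442 women and the chi-square tests stay as they are. The downside is that the trial can no longer claim participant blinding.

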- **Edinburgh Postnatal Depression scale:** Participant’s postpartum depression symptoms will be measured by EPDS, Chinese version. It is an instrument consisting of 10 simple and easily understood items, with rating on a scale from 0 to 3, yielding a total range of 0 to 30. EPDS was developed by Cox et al (1987) and has been widely used for the assessment of postnatal depressive symptoms, but it is not a diagnostic scale for depression, rather a screening tool for those vulnerable to developing depression. The Chinese version of EPDS has been validated and shown to have high sensitivity in detection of postnatal depression. To evaluate the postpartum depressive symptoms, pre (1 month postpartum) and post (2 months postpartum) EPDS will be compared between the two groups.

3 Selection and Withdrawal of Subjects

Study population

To be eligible for inclusion in the RCT, participants must be (1) 18 years of age or older, (2) primiparous mothers, (3) intention to breastfeed, (4) low breastfeeding self-efficacy score (between 14 and 32), (5) singleton pregnancy, (6) term infant (37-42 weeks gestational), (7) Cantonese speaking, (8) HK resident and (9) mother with no serious medical or obstetrical complications.

Participants will be excluded from the study if they fail to meet these criteria and/or if their baby: (1) is <37 weeks gestation, (2) has an Apgar score <8 at five minutes, (3) has a birthweight <2500 grams, (4) has any severe medical conditions or congenital malformations, (5) is placed in the special care baby unit for more than 48 hours after birth, or (6) is placed in the neonatal intensive care unit at any time after birth.

4 Treatment of Subjects

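### No visible text ties an EPDS depression score to a cut-off, a review time or an action, and Section 7 analyses EPDS and BSES-SF at times when they are not measured

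*Combined protocol and SAP*

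**What the plan says.** **Safety.** Section 6 expects no safety problems and adds that "as a precaution, both the delivery of the intervention and participant outcomes will be closely monitored by the PI and the study investigators". It does not say which scores are looked at, when, against what criterion, or what follows.

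**The EPDS.** The Key Measures part of Section 2 says that "it is not a diagnostic scale for depression, rather a screening tool for those vulnerable to developing depression". It adds: "The Chinese version of EPDS has been validated and shown to have high sensitivity in detection of postnatal depression". The use it gives for the scores is that "pre (1 month postpartum) and post (2 months postpartum) EPDS will be compared between the two groups". Background Information says of the first month postpartum: "which is the critical period in sustaining exclusive breastfeeding and are at high risk in developing postpartum depression".

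**Collection.** Under the telephone follow-up heading, "The participants will receive follow-up telephone calls at one, two, four and 6 months postpartum". "The following forms will be completed by a research assistant in the telephone follow-ups", but no form in those lists is named as the EPDS. The self-efficacy form is listed at recruitment and at 2 and 4 months.

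**Identity.** Section 8 gives named data to the PI alone. Section 10 keeps identifiers, including telephone numbers, from the rest of the study team. Section 11 puts only a study ID on the forms and makes the consent form the sole link to the mother.

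**Analysis.** Section 7 applies two-sample t tests to the self-efficacy scores and "EPDS scores between the two study groups at baseline and at 1 and 3 months postpartum". It then compares the same scores by multiple linear regression at 3 months.

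**The concern.** There are two problems, and both concern how the EPDS is handled after it is collected.

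First, the trial gives a sensitive depression screen to mothers chosen because they want to breastfeed but lack confidence. Its own background links failure to breastfeed as planned with postnatal depression. High sensitivity has meaning only at a cut-off, and the protocol adopts none. If the only defined use of a score is a comparison of means, a team can follow every written step and still leave a positive screen unanswered. What is at stake is a mother's access to care.

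Second, the secondary analysis names times at which the scores do not exist. Taken literally, most of the planned comparisons cannot be run. Whoever repairs this after the data are in can choose the time point with the results in view. A rule for reading scores also needs one settled schedule.

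**Working it through.** **1. Is a score tied to a response anywhere?** The whole visible text was read for four elements.

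| Element | Found? | Where |
|---|---|---|
| EPDS cut-off | No | Key Measures gives only the 0 to 30 range |
| Time by which a score is read | No | Section 6 gives no interval |
| Who monitors | Yes, collectively | Section 6: PI and investigators; nobody is assigned individual EPDS scores |
| Referral or escalation step | No | None in any section |

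The route from score to mother is also incomplete. The research assistant completes the follow-up forms. The forms carry an ID only, and only the PI can turn an ID into a person. No step passes a high total from the assistant to the PI, and the other investigators named as monitors could not contact a mother without the PI.

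**2. Do the analysis times match the measurement times?**

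| Time | EPDS measured (Key Measures) | EPDS tested (Section 7) | BSES-SF measured (Key Measures) | BSES-SF tested (Section 7) |
|---|---|---|---|---|
| Baseline | No; no EPDS form at recruitment | Yes | Yes | Yes |
| 1 month | Yes | Yes | No | Yes |
| 2 months | Yes | No | Yes | No |
| 3 months | No call | Yes, plus regression | No call | Yes, plus regression |
| 4 months | No | No | Yes | No |

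- Planned t-test comparisons: 2 scales × 3 times = 6. Those with scheduled data: EPDS at 1 month and BSES-SF at baseline = 2.
- Scheduled measurements: 2 (EPDS) + 3 (BSES-SF) = 5. Those left out of Section 7: EPDS at 2 months, BSES-SF at 2 and 4 months = 3.
- Regressions at 3 months with scheduled data: 0 of 2.

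**3. Scale of the safety gap.** The protocol states no figure here, so there is none to reproduce. Its inputs are N = 442 and two EPDS assessments.

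- EPDS totals at full follow-up: 442 × 2 = 884. Dropout lowers this.
- Mothers at or above a cut-off per assessment, at an assumed 5% to 15%: 0.05 × 442 = 22.1 to 0.15 × 442 = 66.3.
- The nearest figure in the documents is about 20%, in Background Information: 0.20 × 442 = 88.4. It covers pregnancy to 12 months after birth, so it is probably high for a single time point.
- Control mothers, who have no peer counsellor: 442 / 2 = 221, assuming equal arms.

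**The case against.** The strongest reply is that Section 6 already covers this. It names the monitors, and the EPDS is one of the outcomes they must watch closely. A reader might infer from the gap that nobody is responsible; the text does not support that. Responsibility is assigned, but collectively and without a defined task. A reader might also infer that scores would lie unread until follow-up ends. That is hard to square with a promise of close monitoring and with forms completed by a staff member on live calls. The protocol sets no review time, which is a smaller claim than saying that review will be late.

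Other safeguards exist. Both arms receive standard postpartum care, peer counsellors have been taught about maternal illness, and the assistant speaks to each mother. None of these is triggered by a score, the assistant has no written instruction, and the control arm has no counsellor.

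Consent pages and form contents are not in the supplied text, and referral wording could sit in either. This stands as a limit: the claim concerns what the visible protocol says, and Section 6 is where such a rule belongs.

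The numbers are also open to challenge. The 5% to 15% range has no source in the documents, and the high-risk remark concerns the first month, so it does not extend to the 2-month totals. Both objections are fair. The point rests on the missing rule, and the counts only indicate scale.

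The timing mismatch does not prove the safety point. It is a separate error and stands by itself.

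**Conclusion.** Both parts hold. On safety, the protocol makes a general and collective commitment to monitor, but no visible text turns an EPDS score into a reading, a decision or a contact. A positive screen could therefore go unanswered without any breach of the plan. Up to 884 totals are affected, assuming full follow-up. The number of positive screens is unknown, and the range given above depends on assumed rates.

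On analysis, Section 7 is wrong as written and no assumption is needed to show it: four of the six planned comparisons and both regressions have no scheduled data, while three of the five scheduled measurements are not analysed. The documents do not show that Section 7 holds the intended schedule. Key Measures agrees with the call schedule for both scales, and with the form lists for BSES-SF, so Section 7 is the part to change.

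The primary comparison of exclusive breastfeeding is not touched by either part.

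**What to change.** **Section 7.** Test EPDS at 1 and 2 months and BSES-SF at baseline, 2 and 4 months. Move the regression to 2 months for EPDS and to 2 and 4 months for BSES-SF. In the telephone follow-up lists, name the EPDS among the 1- and 2-month forms. This costs a few changed phrases and two form entries, and should be done before any comparison by arm.

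**Section 6.** Add a rule in three steps:
1. The research assistant totals the EPDS at the call.
2. Totals at or above the cut-off in the cited Chinese validation study (reference 22) go to the PI by study ID, without allocation, so that assessors stay blinded. The value must be written into the protocol; the documents do not give it.
3. The PI contacts the mother within a stated number of days, set by the sponsor, and directs her to care.

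Check that the consent wording allows a score to be linked to a mother for this purpose, and amend it if not.

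**Cost.** At the assumed 5% to 15%, flags over both assessments number 0.05 × 884 = 44.2 to 0.15 × 884 = 132.6, with some mothers counted twice. At an assumed 15 minutes each (the protocol's call length), PI time is 44.2 × 0.25 = 11.05 to 132.6 × 0.25 = 33.15 hours.

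**Downside.** Care after a 1-month flag could narrow the 2-month EPDS difference. The narrowing is the difference between arms in flagged proportion × the score reduction in a flagged mother. With assumed differences of 5 to 10 percentage points and reductions of 2 to 4 points, it is 0.05 × 2 = 0.1 to 0.10 × 4 = 0.4 points on the 0 to 30 scale, if care has its full effect by 2 months. That is a small price on a secondary outcome.
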